3. Opportunity Toxicity Toxicity associated with the opportunity cost of time spent on cancer treatment-related medical activities	
 • Time spent on medical appointments as a fraction of time spent at home, on work, leisure, education, childcare, caregiving, and household • Proximity of medical appointment/treatment locations to individual points of interest (home, work, etc.) • Variation of schedule between days with and without a medical appointment
4. Scheduling / Administrative Toxicity Toxicity associated with paperwork, scheduling appointments, dealing with bills and insurance, arrangement to accommodate cancer-related activities	
 • Number of different locations associated with cancer care • Number of appointments per week • Hours per week spent on scheduling and administrative cancer work • Weekly variation in the duration of medical appointments and calls • Variation in time between medical activities

The overall time toxicity score will be a weighted average of the four subtype scores $S_1, S_2, S_3, S_4: T = w_1S_1 + w_2S_2 + w_3S_3 + w_4S_4$ where the weights are constrained to sum to one. We will consider several versions of the time toxicity score defined by the relative weights of the various subtypes. The simplest time toxicity score is one where each subtype is assigned equal weight, and therefore the overall score is a simple average of the population percentiles across the four subtypes. For example, if an individual has subtype scores of 55, 75, 60, and 90, then their time toxicity score will be $(55 + 75 + 60 + 90)/4 = 70$, which suggests that their time toxicity burden is higher than approximately 70% of the population. In some scenarios, it may be appropriate to pre-specify non-equal weights for the different

SOCIAL PROTOCOL (HRP-580)

PROTOCOL TITLE: Time toxicity of cancer: the time demands of cancer-related activities and their impact on well-being and quality of life

VERSION DATE: 02/27/2024

subtypes; for example, personalized time toxicity scores could be generated based on individuals' prior weightings of each subtype, which, for example, might give opportunity toxicity more weight than travel toxicity.

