In addition to pre-specified (equal or unequal) weights, we will also use our daily burden and well-being measures to derive data-driven versions of the time toxicity score. Let M_{ij} denote the daily well-being measure of person i on day j . We will fit the model $M_{ij} = \beta_0 + \beta_2 X_{ij} + \theta_1 S_{1ij} + \theta_2 S_{2ij} + \theta_3 S_{3ij} + \theta_4 S_{4ij} + \epsilon_{ij}$ where X_{ij} represents a set of individual, and day-level covariates, and $S_{1ij}, S_{2ij}, S_{3ij}, S_{4ij}$ are the subtype scores computed for person i on day j . The coefficients $\theta_1, \theta_2, \theta_3, \theta_4$ represent the relative weightings of the subtypes that best predict the mean of M after adjusting for covariates. These coefficients will be standardized to yield weights using the formula $w_k = \theta_k / \sum \theta_k$.

Our proposed approach to deriving time toxicity scores was developed with a view towards how this score may be used in clinical practice going forward. First, computation of the score relies only on time use summary metrics, which could be collected in a variety of ways. While the collection of these metrics is made substantially easier by the app, the time toxicity score could also be applied to time use summary metrics obtained via traditional diary-based recall methods. Second, the four component scores provide easy to understand insights into which types of time use are driving the overall score, and may allow clinicians and patients to better identify interventions (e.g., increased use of telehealth) that could reduce time toxicity. Lastly, the score can be easily adapted to different populations (by re-weighting subtype scores), applied with incomplete data (by using either imputed or complete-case data to compute subtype scores), and computed across a range of time periods.

17.2 Power Analysis:

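### The model for the data-driven weights omits the person effect, and the weight formula has no rule for coefficients of mixed sign, so this version of the score can carry negative weights

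*Combined protocol and SAP*

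**What the plan says.** Section 17.1, Aim 3, builds the overall score T from four subtype scores, "where the weights are constrained to sum to one". No other condition is put on the weights. The worked example averages 55, 75, 60 and 90 to 70, "which suggests that their time toxicity burden is higher than approximately 70% of the population". The plan also states: "We will consider several versions of the time toxicity score defined by the relative weights of the various subtypes". Equal weights are the simplest version.

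For the data-driven versions, daily well-being M for person i on day j is regressed on an intercept, covariates, the four subtype scores and a residual. The predictors "are the subtype scores computed for person i on day j". Then: "These coefficients will be standardized to yield weights using the formula", namely w_k = theta_k / sum(theta_k). The same section says that "the four component scores provide easy to understand insights into which types of time use are driving the overall score", and that the score can be adapted to other populations and to incomplete data "and computed across a range of time periods".

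The Aim 2 model in 17.3, for the same daily well-being data, contains a person-specific random effect b_i. The stated reason is the correlation of repeated measurements. The Aim 2 power simulation in 17.2 uses a residual SD of 1.5 and a within-person correlation of about 0.4.

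**The concern.** There are two separate gaps.

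1. **No person effect.** Two models for the same correlated daily data differ, and no reason is given. Without b_i, stable differences between persons go into the residual, so the theta estimates are less precise. If those differences are related to the subtype scores, the estimates are also biased.
2. **No sign rule.** All measures are oriented so that higher means more burden. That fixes the direction of each score but not the sign of its coefficient. If all four coefficients share a sign, the ratio gives positive weights, even when M is a positive emotion. If signs are mixed, at least one weight is negative. If the sum is near zero, the weights become very large.

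With a negative weight, more of that burden lowers the score. T is then no longer a weighted average on the percentile scale, and the component scores no longer show plainly what drives the total. The score is the Aim 3 primary outcome (3.1), and 17.2 makes its association with the 28-day surveys the main target of inference for that aim. Section 17.3 does not say which version of T enters those regressions.

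**Working it through.** The plan gives no figure for the weights, so the check starts from its variance inputs.

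**Inputs from 17.2, Aim 2.** There are 80 participants and 28 days. Residual variance is 1.5² = 2.25. A correlation of 0.4 implies a person variance of 1.5, since 1.5/(1.5 + 2.25) = 0.4. As a calibration, simulating the Aim 2 power with these values and a two-sided 5% test (assumed) gives 92.7%, against the stated figure of approximately 90%.

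**Precision without b_i.** Let s be the between-person share of a subtype score's variance. Over 28 days the between-person part of its sum of squares is B = s + (1 − s)/28.

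- Without b_i, the variance of theta is proportional to 2.25 + 28 × 1.5 × B.
- With b_i, it is proportional to 2.25/[(1 − B) + λB], where λ = 2.25/(2.25 + 42) = 0.0508.

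| s (assumed) | B | without b_i | with b_i | SE ratio |
|---|---|---|---|---|
| 0 | 0.036 | 3.75 | 2.33 | 1.27 |
| 1/7 | 0.1735 | 9.54 | 2.69 | 1.88 |
| 0.5 | 0.518 | 24.0 | 4.43 | 2.33 |
| 0.8 | 0.807 | 36.2 | 9.62 | 1.94 |

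The share 1/7 is that of the Beta(2,4) distribution, 1/(2 + 4 + 1). The plan uses that distribution for a binary appointment, not for subtype scores. At s = 1/7 the ratio falls to 1.7 or 1.5 if covariates absorb a quarter or a half of the person variance. It reaches 1 only if a score does not vary from day to day.

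**Bias.** In a simulation with a true coefficient of −0.0625 (M coded higher = better) and a person effect correlated 0.3 with a person's mean on that subtype, the average estimate is +0.193 without b_i. It is −0.038 with a random intercept and −0.064 with person fixed effects.

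**What a mixed sign does.** Suppose the coefficients are 0.10, 0.10, 0.05 and −0.05 (assumed). The sum is 0.20 and the weights are 0.5, 0.5, 0.25 and −0.25.

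- The plan's example scores give 27.5 + 37.5 + 15 − 22.5 = 57.5 instead of 70.
- Scores of 90, 90, 90 and 10 give 45 + 45 + 22.5 − 2.5 = 110, which is off the scale.

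**How often.** This needs an effect size and a correlation between subtypes. The documents give neither for the subtype scores. With four equally harmful subtypes, correlation 0.5 and s = 1/7, runs with at least one negative weight are:

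| Effect per composite SD | as written | with b_i |
|---|---|---|
| 0.12 units | 87% | 65% |
| 0.25 units | 60% | 13% |
| 0.50 units | 11% | 0.1% |

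At 0.25 units, T leaves 0 to 100 for at least one participant in 16% of runs as written and 0.3% with b_i. Power for the plan's 0.4 SD effect is 97% with equal weights, 92% as written and 96% with b_i.

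With s = 0.5 and a harm of 0.0625 per SD for each subtype, the rates are 88% and 49%. The 95% range of a weight whose true value is 0.25 is then −2.67 to 2.14 as written, and −0.25 to 0.71 with b_i.

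**Unequal harm.** If only one or two of the four subtypes are harmful, a negative weight occurs in about 80 to 94% of runs even with b_i. It falls mostly on the null subtypes. With one harmful subtype at 0.25 units, that subtype itself gets a negative weight in about 0.2% of runs as written.

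**The case against.** The strongest reply has four parts.

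- **The rates depend on the assumed truth.** This stands. They run from near 0% to over 90% with effect size, correlation and between-person share, so they are illustrations. The 1.88 also rests on a share that the plan never states for subtype scores.
- **Data-driven weights exist for unequal harm.** This also stands. A reader might infer that they add little beyond equal weights. That follows only when the subtypes are equally harmful. With one harmful subtype at 0.25 units, data-driven weights give 92 to 97% power, against 83 to 84% for equal weights. At 0.12 units the model as written does lose, with 73% against 83%.
- **Omitting b_i does not create the sign problem.** A reader might infer that it does, and that adding it is enough. It makes negative weights more frequent when several subtypes are harmful, but they remain with b_i, so the sign rule is needed in its own right.
- **A random intercept has a cost.** The weights then rest mainly on within-person variation: at s = 1/7 the between-person part of the information is 0.0088/0.8353, about 1%. Yet 17.3 uses T to compare persons. This is a fair reason to report both kinds of coefficient, but the plan does not give it as a reason for leaving b_i out.

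The documents do not support reading this as a failure of Aim 3. The equal-weight score is untouched, and in the equal-harm illustration at 0.25 units power stays above the plan's 80%.

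**Conclusion.** The point holds for the data-driven versions of the score only. It should be fixed, but it does not threaten the study.

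Both gaps are plain in the text. Omitting b_i costs precision by a factor of roughly 1.3 to 2.3 in the standard error, for between-person shares from 0 to 0.8 and with no person variance absorbed by covariates. It adds bias if person effects are related to the scores. The weight formula permits negative weights and values of T outside 0 to 100. How often this would happen cannot be settled from the documents: about 60% as written and 13% with b_i is one illustration under equal harm.

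Confidence is high for the gaps and for the direction of their effect, and low for any single rate.

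**What to change.** 1. **Add the random intercept b_i** to the 17.1 weight model, as in 17.3. Report within-person and between-person coefficients as a check, because T is later used between persons.
2. **Pre-specify a rule for mixed signs or a sum near zero.** Examples are constraining each theta_k to the harmful direction of the chosen M, or falling back to equal weights. State the downside: a constraint assumes that no subtype is protective. The rule may act often, in 13% of runs in the equal-harm illustration at 0.25 units with b_i, and more often if some subtypes are null.
3. **Complete the definitions at the same time.** Name M, since 17.3 lists six measures plus the U-index, and give its harmful direction. Define the daily subtype score: nine of the 16 measures in Table 2 are stated per week, and three variation measures, such as "Variation of schedule between days with and without a medical appointment", have no single-day value. Say which version of T enters the Aim 3 regressions in 17.3.

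The cost is plan wording and code, with no new data. The rule should be fixed before the estimated signs are seen, because a choice made afterwards would be post hoc.

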Demographics: Demographic characteristics collected will include age, sex, race/ethnicity, household income, education, insurance status, relationship status, parenting and caregiver status, employment status, and zip code to assess rurality and distance from clinic.

General Quality of Life: QOL is a multi-dimensional concept including domains of physical, psychological, social health, and overall life satisfaction.[27] We will measure QOL using the Functional Assessment of Cancer Therapy - General (FACT-G) questionnaire (39 items).[31]

Depression and Anxiety: Symptoms of anxiety and depression will be measured using the Hospital Anxiety-Depression Scale (HADS). This measure consists of 14 items rated on a 4-point scale and provides separate scores for anxiety and depression, including cut-offs for potentially clinically relevant anxiety and depression.

Distress: We will measure cancer-related distress using the National Comprehensive Cancer Network Distress Thermometer, a single-item tool measuring distress on a scale from 0-10 with an accompanying problem list of potential contributing issues, including practical, physical, family, emotional, and spiritual concerns.[33, 34]

Symptom Management: Breast and ovarian cancers and their treatments can result in significant side effects and symptom burden for patients and these symptoms can increase healthcare utilization while decreasing QOL. The MD Anderson Symptom Inventory (MDASI) is a multi-symptom patient-reported measure of 13 core symptoms that are common and often severe, with impacts on functioning, in patients with cancer.[35]

Opportunity Costs: The Oncology Opportunity Cost Assessment Tool (OOCAT) evaluates opportunity costs - including time spent seeking care, lost wages, lost leisure time, and other indirect costs associated with seeking cancer care.[36] The 18-item instrument includes six domains: travel, appointments, work and school, home, health system, and caregiver burden.

Work, Insurance and Financials: We will measure financial toxicity using the Comprehensive Score for Financial Toxicity (COST) instrument, an 11-item questionnaire validated in individuals with cancer.[37] We will also measure current employment status, days missed due to illness, and health insurance coverage using

SOCIAL PROTOCOL (HRP-580)

PROTOCOL TITLE: Time toxicity of cancer: the time demands of cancer-related activities and their impact on well-being and quality of life

VERSION DATE: 02/27/2024

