Associations between time use and daily well-being measures will be quantified via longitudinal regression modeling. We will use generalized linear mixed models to describe the longitudinal relationship between daily time use summary measures (calculated in Aim 1) and self-reported daily well-being. Separate models will be fitted for each of the six daily well-being measures along with an overall well-being score, the U-index.[50, 51] Models will be of the form $g([E(W_{ij}^{(r)})]) = \beta_0 + \beta_1 T_{ij} + \beta_2 X_{ij} + b_i + \epsilon_{ij}$ where $W_{ij}^{(r)}$ is the r th well-being measure (e.g., Happy, Sad, Stress) reported by person i on day j ; g is a function depending on the regression model type; b_i is a person-specific random effect, and ϵ_{ij} is the residual. The predictors of interest T_{ij} are a vector of daily time use measures (time spent on medical appointments, number of medical-related phone calls, etc.). X_{ij} is a vector of covariates for adjustment including both individual-level (age, race, cancer type, etc.) and day-level (day of the week, time of year, time since initiation of the current round of treatment, etc.) factors. Mixed models are chosen to account for correlation of repeated measurements over the course of the 28-day mobile data collection period. The main output from these analyses will be inference about the coefficients in β_1 , which summarize the association between time use measures and self-reported well-being. In addition to models of the type presented above, which correlate well-being with time use on the same day, we will also fit models using time use summary measures that aggregate time use longitudinally. These models will allow us, for instance, to assess whether aggregated cancer-related time use over the past week is a stronger predictor of daily well-being than time use on the current day only.

Defining and exploring the role of context as an effect modifier. We will use quantitative and qualitative approaches to understand the role of context in

SOCIAL PROTOCOL (HRP-580)

PROTOCOL TITLE: Time toxicity of cancer: the time demands of cancer-related activities and their impact on well-being and quality of life

VERSION DATE: 02/27/2024

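### The Aim 2 mixed model does not separate within- from between-person time use, so the past-week versus current-day comparison can wrongly favour the weekly measure

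*Combined protocol and SAP*

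**What the plan says.** Section 17.3 (Aim 2) models each daily well-being measure on a vector of daily time-use measures T and covariates X, plus a term b that "is a person-specific random effect". The reason given for this structure is correlation alone: "Mixed models are chosen to account for correlation of repeated measurements over the course of the 28-day mobile data collection period". The product is a set of coefficients "which summarize the association between time use measures and self-reported well-being".

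The section then adds that "we will also fit models using time use summary measures that aggregate time use longitudinally". One question offered as an example is "whether aggregated cancer-related time use over the past week is a stronger predictor of daily well-being than time use on the current day only". It does not write the aggregated model out (I assume the same random-effect form) and gives no criterion for a stronger predictor.

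No section mentions person-mean centring, a person-mean covariate, fixed effects or any other split of within- from between-person association. Age, race and cancer type are named as examples in an open list of individual-level covariates. Symptom burden, baseline quality of life and usual time use are not named.

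Two other places bear on the point. Section 5.2, on symptom measurement, says that "these symptoms can increase healthcare utilization while decreasing QOL". Section 2.2 reports the group's own finding, in patients with breast cancer, that heavier time and workload burdens went with worse psychosocial outcomes and lower quality of life.

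**The concern.** A random intercept allows for correlation among a person's days. It does not remove correlation between that person's underlying well-being and usual time use. With raw T in the model, the single coefficient is a weighted average of two associations: how a person's well-being differs between their own heavier and lighter days, and how heavier users differ from lighter users.

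The weights depend on how much of the exposure's variance lies between people. A rolling 7-day sum averages out day-to-day variation, so its between-person part is much larger than that of a same-day measure. The two coefficients being ranked are therefore different mixtures. If heavier users have lower well-being for other reasons, such as symptom burden, the weekly measure can look stronger because it better identifies who the patient is, with no accumulation of burden from day to day. At stake is the reading of the past-week versus current-day result.

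**Working it through.** **Inputs.** From section 17.2 (Aim 2): 80 participants, 28 days, daily appointment probability p from Beta(2,4), residual SD 1.5, within-person correlation about 0.4. Assumed: two-sided 5% level; days 7-28 (22 days), since a full past week exists only from day 7; independent visits given p; no covariates; and a correlation rho between p and the random intercept of 0, -0.3 or -0.5. The documents give no value for rho.

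**The plan's own figure.** Var(p) = 8/252 = 0.0317 (SD 0.178) and E[p(1-p)] = 1/3 - (0.0317 + 0.1111) = 0.1905. The standard error of the same-day effect is 1.5/sqrt(80 x 27 x 0.1905) = 0.0740. Power for 0.25 units is Phi(0.25/0.0740 - 1.96) = 92%. The plan says approximately 90%, so the set-up agrees and I do not dispute that figure.

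**Variance shares** (variance of person means over total variance, 22 days):
- Same-day: person means 0.0317 + 0.1905/22 = 0.0404; total 0.0317 + 0.1905 = 0.2222; share 18%.
- 7-day sum: the 22 overlapping windows weight the 28 days 1 to 6, then 7 sixteen times, then 6 to 1, with sum of squares 966. Person means: 49 x 0.03175 + 0.1905 x 966/22^2 = 1.936. Total: 49 x 0.03175 + 7 x 0.1905 = 2.889. Share 67%; the simulated average is about 66%.

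**Weight on the between-person slope.** The intercept variance is 2.25 x 0.4/0.6 = 1.5. Between-person variation enters the fit with factor 2.25/(2.25 + 22 x 1.5) = 0.0638.
- Same-day: 0.0638 x 0.0404/(0.1818 + 0.0638 x 0.0404) = 1.4%.
- Weekly: 0.0638 x 1.936/(0.953 + 0.0638 x 1.936) = 11.5%.

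So about 88% of the information in the weekly fit is still within-person, and the within-only variance is 1/(1 - 0.115) = 1.13 times larger.

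**Bias with no true effect, rho = -0.3.**
- Weekly: the between-person slope is -0.3 x 1.225 x 7 x 0.178/1.936 = -0.237, so the bias is 0.115 x -0.237 = -0.027 per visit. The standard error is sqrt(2.25/(80 x 22 x 1.077)) = 0.0345, so the test is shifted by 0.79 standard errors and rejects in about 12% of studies.
- Same-day: the slope is -0.3 x 1.225 x 0.178/0.0404 = -1.62, so the bias is 0.014 x -1.62 = -0.023. The standard error is sqrt(2.25/(80 x 22 x 0.1844)) = 0.083, the shift is 0.27, and the test rejects in about 6%.

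At rho = -0.5 the shifts scale by 5/3, to 1.31 and 0.45, giving about 26% and 7%.

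**Simulation with fitted random-intercept models:**

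| Result | rho 0 | rho -0.3 | rho -0.5 |
|---|---|---|---|
| No effect: weekly significant | about 5% | 11-14% | 24-25% |
| No effect: same-day significant | about 5% | 4-6% | 7-9% |
| Only same-day matters (-0.25): weekly model fits better | 4-6% | about 10% | 15-16% |
| Same setting: weekly coefficient x 7 (truth -0.25) | -0.27 | -0.45 | -0.59 |

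Ranges cover repeated simulations. With 500 runs the Monte Carlo error is at most about sqrt(0.25 x 0.75/500) = 1.9 points for these rates. Fit was judged by maximised log-likelihood.

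**After within-person centring.** Weekly false positives return to 4-6%, the coefficient x 7 to -0.25 to -0.27, and wrong preference for the weekly measure to about 5%, at every rho tried.

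**Sensitivity.** If visits follow a mostly fixed weekly schedule (a second assumption), the variance shares become 13% and 85%. Weekly false positives become 27%/65%, and wrong preference for the weekly model 13%/31% against 4% at zero correlation. With rho = +0.3, independent visits and a same-day effect of -0.25, the weekly coefficient x 7 shrinks to about -0.07.

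**The case against.** The plan speaks of association and prediction and never claims a within-person effect. For prediction, between-person information is legitimate: a patient whose weeks are always heavy and whose well-being is low is correctly predicted by past-week use. This stands as far as it goes. But a contrast of past week with current day invites a reading about timing or accumulation, and only the within-person part can support that.

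A reader might infer three stronger things, none of which the documents support.
- That the conclusion will be biased towards accumulated burden. Sections 2.2 and 5.2 support the direction of the correlation, not its size. Only correlation left after adjustment matters, and symptom, quality-of-life and mood scores are collected at baseline and could enter the open covariate list.
- That the weekly measure would usually win. When only same-day use matters, same-day still fits better in at least 84% of runs at the correlations tried with independent visits.
- That the whole Aim 2 analysis is undermined. The sentence beginning "The main output from these analyses will be inference about the coefficients" precedes the aggregated models and concerns the same-day ones, where the between-person weight is about 1.4%. The past-week comparison is offered as one example of additional models.

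It is also fair that the remedy costs precision. The label of hypothesis generation does not answer the point, because section 17.3 attaches it to the effect-modification analysis.

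**Conclusion.** The concern holds in conditional form. As written, the models blend within- and between-person associations, far more so for the weekly measure, and the comparison can wrongly favour it if heavier users have lower underlying well-being after adjustment. At assumed correlations of -0.3 to -0.5, false significance of the weekly coefficient is roughly two to five times the nominal 5%, while wrong preference for the weekly model rises more modestly, by about 4 to 12 points. At zero correlation there is no bias, and with the opposite sign the weekly coefficient shrinks or reverses. The sizes rest on the assumed correlations, the absence of covariates, independent visits and the assumed form of the aggregated model.

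**What to change.** In section 17.3 (Aim 2), above all for the aggregated measures:
- Enter each time-use measure as the person's mean over the analysed days plus the daily deviation from it, and report both coefficients.
- Base the past-week versus current-day comparison on the deviation coefficients, and state the criterion for a stronger predictor.
- Fit both models on the same days, those with a complete past week.

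This adds one covariate per exposure and no data collection. Same-day results change little (variance 1/(1 - 0.014) = 1.01 times larger). The weekly measure loses precision: variance is about 1.13 times larger under the plan's inputs. With the fixed weekly schedule above, it is 1 + 0.0638 x 0.85/0.15 = 1.36 times larger, and another assumed regular schedule gave about 1.6. Reporting the person-mean coefficient keeps the between-person information in view. The split removes stable differences between people only; confounding that varies from day to day, such as a symptom flare that prompts a visit, remains.
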